5.3.2 Eligibility Criteria

Inclusion Criteria:

1. Men, ages 21-50;
2. Able to read English and to complete study evaluations;
3. Heavy (also known as risky, high-risk, or hazardous) alcohol use, defined as 15-70 standard drinks per week on average over the past 30 days;
4. No more than 3 days/week of alcohol abstinence in the past 30 days, to maximize likelihood that participants will choose to drink during the laboratory sessions.
5. At least 1 heavy drinking day (\geq 5 drinks/day) per week on average during the 30 days prior to screening.

Exclusion Criteria:

[figure not shown]
1. Individuals who are seeking AUD treatment or have been in treatment within the past 6 months;
2. Current DSM-V non-alcohol substance use disorder other than tobacco and marijuana;
3. Positive urine drug test results at more than one baseline appointment for opioids, cocaine, benzodiazepines, or barbiturates;
4. Regular use of psychoactive drugs including antipsychotics, anxiolytics and antidepressants during the 30 days prior to entry, as well as anticonvulsants, beta blockers, central nervous system stimulants or depressants, or other drugs that cause excessive sedation;
5. Psychosis or any other serious mental illness as judged by MINI and study physician assessment;

6. Medical conditions that in the judgment of the study physician contraindicate the consumption of alcohol or would make study participation hazardous;
7. History of serious alcohol withdrawal (e.g. seizures, DTs, hospitalization) or a Clinical Institute Withdrawal Assessment Scale (CIWA-AD) score ≥ 8 ;
8. Participants who report disliking beer will be excluded because beer will be provided during the alcohol self-administration periods.

6. METHODS

The study will consist of the following steps, replicating the Yale ADP methods:

- (1) Recruitment;
- (2) Pre-screening: Brief telephone or in-person to determine eligibility for full screening beginning with establishing non-treatment seeking status;
- (3) Full Screening/baseline visit: 1-3 in-person visits to obtain consent and to evaluate eligibility (e.g. to reject participants with medical conditions): participants who meet *heavy drinking criteria*, and by confirming that the individual is *non-treatment seeking*. If these criteria are met, physical examination and laboratory testing will be conducted. Eligible participants then proceed to the main part of the study, which includes participation in 2 human lab sessions and 6 AABM training sessions.
- (4) Human Lab ADP Sessions 1 and 2: There will be two sessions, Human Lab/ADP Session 1 (Pre-training), and Human Lab/ADP Session 2 (post-training). Alcohol Drinking Paradigm (ADP): After the alcohol cue-induced craving, subjects will be given the opportunity to self-administer alcohol using the ADP. (**Table 1**) Subjects are first given a moderate Priming Drink of alcohol at 11 AM, designed to raise blood alcohol to ~ 0.03 mg%, and are instructed to drink it within 5 minutes. At 1 PM, and again at 2 PM, subjects undergo two 1-hour long alcohol Self-Administration (SA) periods. For each SA period, a tray of 4 beer drinks (each containing an amount of alcohol calculated to increase blood alcohol concentration by 0.015 mg%) will be brought into the Lab room along with a "tab" sheet worth \$12. Participants are told that these 4 drinks will be available for the next 60 minutes, and they can choose to drink or keep the money; each drink will cost \$3. The money will be given by check at the end Human Lab Sessions. This monetary cost for each drink was determined to reliably reflect the trade-off between desire to drink and cost^{20,21}. **The main measure is the number of drinks consumed over the course of two 1-hour-long SA periods**. [name] at Yale University helped to develop the ADP, and it has been adopted by other prominent research groups²²⁻³³.
- (5) Phone Visits 1 and 2: After each Human Lab ADP session, a study coordinator will call the participant to check in by phone.
- (6) Alcohol Approach Bias Modification (AABM) training: Immediately following completion of Human lab Session 1, patients will be randomly assigned to receive 6 sessions of AABM training over 2 weeks beginning 2-7 days after Human Lab/ADP Session 1. We will use a training version of the Alcohol Approach-Avoidance Task: patients are asked to respond to the format of presented pictures using a joystick (push right-tilted pictures, pull left-tilted pictures), irrespective of the pictures' content. Pushing a picture away decreases picture size; pulling a picture closer increases size (zoom effect). There are 2 categories of pictures; 20 different alcoholic and 20 different non-alcoholic beverages. Training effect is achieved by presenting alcohol pictures in push format only and non-alcoholic drinks in pull format only. 200 trials are presented per session (~ 20 minutes) with a short break halfway through.
- (7) Participants then undergo a Follow-up visit 1 week after the last ADP session, where adverse events and alcohol use will be assessed and a research clinician will provide a motivational enhancement session to encourage these non-treatment seeking participants to consider treatment and provided with referral materials.

6.1 Treatment – Computerized Training

6.1.1 Identity of Investigational Treatment

The Alcohol AAT is a joystick-task that measures automatic approach tendency toward alcohol. The proposed Alcohol AAT was developed based on the previous work of Wiers et. al., (2009)^{10,12} and Rink et al., (2007)⁵⁰.

6.1.2 Dosage, Administration Schedule

Patients are instructed to respond to the format of presented pictures using a joystick (push right-tilted pictures, pull left-tilted pictures), irrespective of the pictures' content. Pushing the picture away decreases picture size, while pulling a picture closer increases size (zoom effect). There are 2 categories of pictures; 20 different alcoholic and 20 different non-alcoholic beverages (soft drinks). Patients are instructed to either push or pull for left-tilted images and to perform the alternative response for right-tilted images. All images are presented in both formats. The difference in reaction times (RT) between push and pull is the approach bias. The task starts with 10 practice trials showing neutral objects (containers), followed by 80 test trials. A standardized d-score is calculated which represents differences in reaction time for pushing vs. pulling⁷⁵. Negative values indicate less alcohol-approach bias⁷⁵.

6.1.3 Method of Assignment/Randomization

All participants will receive the active AABM training intervention.

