3.2 Purpose of Study/Potential Impact

We will conduct the first pilot trial of AABM effects on alcohol consumption in the human laboratory in non-treatment-seeking, heavy-drinking individuals and the first trial of AABM effects on the Yale Alcohol Drinking Paradigm - a method of rapidly assessing the potential efficacy of putative pharmacologic and possibly behavioral treatments for AUD. Participants will be 12 non-treatment-seeking heavy-drinking male volunteers. After baseline assessment, participants will undergo Human Lab session 1, in which we will administer the Alcohol Approach-Avoidance Task (AAT) (not AABM training) to measure baseline (pre-treatment) alcohol approach bias tendency, and then conduct the ADP to measure baseline alcohol consumption. After Human Lab/ADP Session 1, participants get 2 weeks of a total of 6 sessions of training; they will have been randomly assigned to undergo AABM or a sham training condition. Outcomes will be various measures of feasibility, including recruitment, retention, safety, and adverse effects and assessment of measurement burden, and the tolerability of ADP and AABM interventions

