6.1.4 Blinding and Procedures for Unblinding

Not applicable

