6.2.1 Efficacy

This is a pilot feasibility study, not an efficacy study. The primary outcome variables are measures of feasibility:

1. Time needed to recruit, screen, and run the study procedures for 12 participants.
2. Retention rates at the various in the study process (screening, Human Lab ADP session 1 + 2, AABM/sham training sessions 1-6, and follow-up).

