6.3.5 On study visits

Baseline/screening visit 4 hours	Informed consent + HIPAA Participant Locator form Demographics Eligibility form Medical History Physical Exam Lab tests Height/weight Concomitant Medications Columbian Suicide Severity Rating Scale AE Spontaneous Breath alcohol test Structured Clinical Interview for DSM-5 (SCID) Timeline Followback (TLFB) Clinical Institute Withdrawal Assessment (CIWA-AD) Urine Drug Screen (UDS) Barratt Impulsiveness Scale (BIS-11) Alcohol Use Disorders Identification Test (AUDIT) Alcohol Purchase Task (APT) Obsessive Compulsive Drinking Scale (OCDS) Vitals Balloon Analogue Risk Task (BART) Delay Discounting (DD) Iowa Gambling Task (IGT) Salience Task
Phone Visits 1 and 2 10 minutes each	AE Spontaneous Timeline Followback (TLFB)
Human Lab Sessions 1 and 2 12 hours each human lab	Weight AE Spontaneous Concomitant Medications Breath alcohol test Timeline Followback (TLFB) Clinical Institute Withdrawal Assessment (CIWA-AD) Urine Drug Screen (UDS) Blood alcohol level (BAL) Vitals Alcohol Urge Questionnaire (AUQ) Biphasic Alcohol Effects Scale (BAES) Balloon Analogue Risk Task (BART) Delay Discounting (DD) Ratings of Drinking Behavior During the Alcohol Self-Administration Period
AABM/Sham Training Sessions 1-6 30 minutes each visit	Concomitant medications AE Spontaneous Breath alcohol test TLFB (Sessions 2, 5, and 8 only) CIWA-AD AABM/Sham training
AABM/Sham Training Sessions 1 and 6 an additional 1.5 hours	Obsessive Compulsive Drinking Scale (OCDS) Alcohol Purchase Task (APT) Iowa Gambling Task (IGT) Delay Discounting (DD) Balloon Analogue Risk Task (BART)

	Barratt Impulsiveness Scale (BIS-11) Stop Signal Task (SST)
Follow-up Visit 1 hour	Breath alcohol test Timeline Followback (TLFB) Concomitant medications AE Spontaneous Medical Management (MM) Participant End of Study Questionnaire

Assessments at Study Entry and During and After Human Lab Sessions

At Entry:

These are adapted from previous/ current clinical studies at the UCSF/SFVAMC Addiction Research Program.

- Demographic data, will be assessed with data on age, race, socioeconomic status, marital status, educational and occupational levels, and significant medical history.

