- A number of safety evaluations are included: Medical history and physical examination; Suicide Risk Assessment: The Columbia Suicide Severity Rating Scale [101]. It is a standard, thorough, frequently used method to screen for suicidal ideation, used by our group in alcohol use disorder clinical trials;
- Clinical Laboratory Tests for Health/Safety Monitoring: Blood samples will be collected for chemistry, liver panel, renal panel and complete blood count (CBC); urine will be collected for urinalysis.
- Structured Clinical Interview for DSM5, (SCID) [96]: the SCID will be used to determine DSM-V diagnosis of current (current year) Alcohol Use Disorder, and the DSM-V current psychiatric diagnoses for anxiety, mood, psychotic, and non-alcohol substance use disorders in order to determine study eligibility.
- Study Physician Review: All health measures, medical history/exams and labs will be reviewed by a study physician to ensure that the subject meets all the eligibility criteria and are ready for randomization
- Alcohol Approach Task (AAT): A way to measure pre-treatment alcohol approach bias tendency. Salience Task: A survey that measures the salience of each stimulus image for participant.

At Entry and at various times throughout the study:

- Clinical Institute Withdrawal Assessment for Alcohol, DSM-IV Version (CIWA-AD): at entry and before each Human Lab Session and at each Follow-up;
- Urine Drug Screen: For opioids, benzodiazepines, cocaine, amphetamines, cannabis, barbiturates: at entry and before each Human Lab Session.
- Breath alcohol concentration (BrAC); at entry and before each Human Lab Session; and during each Human lab Session
- Vital Signs: Temperature, heart rate, and blood pressure will be measured at study entry and multiple times during each Human Lab Session.
- Concomitant Medications Review: at entry and before each Human Lab session: thorough review of all concomitant medications (prescription or over-the-counter) in the past 30 days, as well as those started during the study.
- Concomitant Treatment Log: At Entry and A way to track any type of alcohol treatment at baseline/screening and throughout the study.

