6.4.3.1 Primary Analyses

Primary analyses will consist of descriptive statistics. These measures of feasibility are:

1. Time needed to recruit, screen, and run the study procedures for 4 participants
2. Retention rates at the various timepoints in the study process (screening, Human Lab ADP session 1,2,3, and follow-up).

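### The protocol describes both a randomised sham-controlled design and a single-arm design, and the planned primary analysis in 6.4.3.1 does not match the primary outcomes in 5.2.1 and 6.2.1

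*Combined protocol and SAP*

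**What the plan says.** **Text that implies two arms.** Section 3.2 says that after the first ADP session participants enter training and "they will have been randomly assigned to undergo AABM or a sham training condition". Step (6) of the Methods says "patients will be randomly assigned to receive 6 sessions of AABM training over 2 weeks", but names no alternative condition. Section 6.2.1 defines retention over stages that include "AABM/sham training sessions 1-6, and follow-up". The visit table in 6.3.5 has a block headed "AABM/Sham Training Sessions 1-6", and the study physician's review in the same section checks that the participant "meets all the eligibility criteria and are ready for randomization".

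**Text that implies one arm.** Section 6.1.3, the section that exists to define assignment, says "All participants will receive the active AABM training intervention". Section 6.1.4, on blinding, says "Not applicable". Section 5.1 largely repeats the paragraph in 3.2 but stops before the randomisation clause. The completion target in 5.3.1 and the schedule in 6.3.1 name only alcohol approach bias modification (AABM) sessions. The two training descriptions, in step (6) and in 6.3.5, describe active training only.

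**Planned primary analysis.** Section 6.4.3.1 lists "Retention rates at the various timepoints in the study process (screening, Human Lab ADP session 1,2,3, and follow-up", with no training sessions. It also gives the recruitment and running time for 4 participants.

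**The concern.** The number of arms is the most basic fact of the design, and 3.2 and 6.1.3 cannot both be true. Staff who follow the 6.3.5 visit table and the physician review would expect to randomise participants and deliver a sham task that is not described anywhere. A reader of 3.2 would expect a sham comparison that 6.1.3 rules out.

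The second fault concerns the primary outcomes. Section 5.2.1 makes retention through the training sessions part of the primary outcome. The analysis section that should report it leaves those sessions out, includes a session that the study does not hold, and gives a different number of participants. An analyst working from 6.4.3.1 alone would not report the primary outcomes that 5.2.1 defines.

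**Working it through.** The plan derives no sample size, power or error rate (6.4.1 and 6.4.2), so there is no figure of its own to reproduce. The check is a comparison of texts.

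**Step 1: count the sham and randomisation wording about this study.**

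| Place | Random assignment | Sham | Total |
|---|---|---|---|
| 3.2 | 1 | 1 | 2 |
| Methods, step (6) | 1 | 0 | 1 |
| 6.2.1 | 0 | 1 | 1 |
| 6.3.5, visit table | 0 | 3 | 3 |
| 6.3.5, physician review | 1 | 0 | 1 |
| Sum | 3 | 5 | 8 |

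This gives 3 + 5 = 8 mentions in 5 places. The count excludes the heading of 6.1.3, the account of earlier published trials in section 2.2.1, and the reference list.

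**Step 2: look for what a sham arm would need.** Sections giving the content of a sham task: 0. Sections giving an allocation ratio or a method for the sequence: 0. Sections planning a summary by arm: 0. Section 6.1.2 does describe a version of the task with every image shown in both formats. However, it goes on to define the approach-bias score over 80 test trials, so it describes the measurement task and is not labelled as a sham.

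**Step 3: set the three statements of the primary outcomes side by side.**

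| Element | 5.2.1 | 6.2.1 | 6.4.3.1 |
|---|---|---|---|
| Participants in the time outcome | 12 | 12 | 4 |
| Screening | yes | yes | yes |
| ADP sessions | 1, 2 | 1, 2 | 1, 2, 3 |
| Training sessions | AABM 1–6 | AABM/sham 1–6 | none |
| Follow-up | yes | yes | yes |

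Sections 5.2.1 and 6.2.1 list the same stages and differ only by the added word sham. Section 6.4.3.1 differs in substance. The retention outcome in 5.2.1 covers 1 + 2 + 6 + 1 = 10 stages. Section 6.4.3.1 lists 1 + 3 + 1 = 5, one of which (ADP session 3) is not in the design, so it covers 4 of the 10.

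**Step 4: check the number of ADP sessions elsewhere.** Section 5.2.2, Methods step (4), the schedule in 6.3.1 and the secondary analyses in 6.4.3.2 all have two. Only 6.4.3.1 has three.

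**Step 5: ask whether the two faults are one.** They are not. Removing every sham and randomisation mention would leave 6.4.3.1 still without the training sessions, and still with a third ADP session and 4 participants.

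**The case against.** The best defence is that the study is plainly single-arm and the rest is leftover wording. The sections on assignment and blinding agree with each other and with 5.1, 5.3.1, 6.3.1, the payment table and both training descriptions. The absence of any sham task suggests a deleted arm rather than a live one. As analysis is descriptive, there is no test or between-arm comparison to corrupt. Most of this stands, and it makes the single arm the likelier reading. It does not remove the need for correction, because no section says that the sham text is superseded and it remains in the visit table and the physician review.

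A reader might infer more than the documents support in three respects:

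- **That the retention outcome exists in three conflicting forms.** On a single-arm reading, 5.2.1 and 6.2.1 become the same once the word sham goes. The substantive mismatch is 6.4.3.1 alone.
- **That a single arm defeats the purpose in 2.1,** which speaks of the feasibility of controlled trials. A pilot can inform later controlled trials without a control arm, and 2.1 and 3.1 both look to future studies. The process aims in 4.2 can be met with one arm, so 2.1 needs no rewording.
- **That the secondary aim is an unsupported efficacy claim.** Section 6.2.1 disclaims an efficacy purpose, 6.4.1 excludes inference, and 4.3 calls the assessment preliminary. What remains is a minor wording point: without a comparator, a change from ADP session 1 to session 2 is confounded with time and repeat exposure.

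**Conclusion.** The concern holds in two separate parts, and both must be fixed.

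1. The protocol contradicts itself on the number of arms. Eight mentions in five places conflict with 6.1.3 and 6.1.4, and nothing needed to run a sham arm is specified. The weight of the text favours a single arm. That is a judgement from the documents, which do not settle it.
2. The planned primary analysis in 6.4.3.1 disagrees with 5.2.1 and 6.2.1 on three items: the training sessions (none against six), the ADP sessions (three against two) and the participants (4 against 12).

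The size is textual. No power, error rate or planned comparison changes. The attribution wording in 4.3 and 3.3.1 is minor and would not require an amendment by itself. The conclusion assumes that all the sections cited are current text, and nothing in the document indicates otherwise.

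**What to change.** The sponsor should confirm one design and state it throughout.

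**If single-arm:** delete the randomisation and sham wording in 3.2, Methods step (6), 6.2.1, the 6.3.5 visit table and the physician review. As a one-line change, describe the secondary aim in 4.3 and the early-signal sentence in 3.3.1 as a descriptive within-participant change from ADP session 1 to session 2, which cannot be attributed to AABM without a comparator. The cost is amendment wording and somewhat more modest claims.

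**If two arms are intended:** correct 5.1, 6.1.3 and 6.1.4, and bring the sections that now name AABM only into line. Specify the allocation method and ratio, the content of the sham task, who is blinded, and descriptive summaries by arm. This is more than wording, because those procedures do not yet exist in the protocol.

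**In either case:** align 6.4.3.1 with 5.2.1. The time outcome should refer to 12 participants. Retention should be reported at screening, ADP sessions 1 and 2, training sessions 1–6 and follow-up, with the training sessions named to match the confirmed design. This costs wording only.

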6.1.4 Blinding and Procedures for Unblinding

Not applicable

6.1.5 Packaging/Labelling

Not applicable

6.1.6 Concomitant Therapy

Participants will be informed that they cannot use psychoactive drugs including antipsychotics, anxiolytics and antidepressants during the 30 days prior to entry, as well as anticonvulsants, beta blockers, central nervous system stimulants or depressants, or other drugs that cause excessive sedation in the judgment of the study physician/PI. Additionally, if participants engage in treatment for alcohol use disorder while enrolled in the study, then they will be withdrawn as they are no longer considered eligible.

6.1.7 Restrictions

As per Exclusion Criteria, above.

6.2 Assessments

Please see the list of study measures below, Sec. 6.3.5

6.2.1 Efficacy

This is a pilot feasibility study, not an efficacy study. The primary outcome variables are measures of feasibility:

1. Time needed to recruit, screen, and run the study procedures for 12 participants.
2. Retention rates at the various in the study process (screening, Human Lab ADP session 1 + 2, AABM/sham training sessions 1-6, and follow-up).

6.2.2 Safety

Please see the study procedures, below, Sec. 6.3.5, and steps to minimize risks, above, in Sec.3.3.5.

6.2.2.1 Adverse Events Definition and Reporting

Adverse Events

During the study, site personnel will note any change in the condition(s) and the occurrence and nature of any adverse events. Important clinical information that comes to light during study participation will be communicated by research coordinators to the study physician in real time.

The study physician (either the PI, [name]) will review each participant's safety at each study visit.

- Lab results will be reviewed on the same day that the results are received.
- Adverse effects reported by participants will be reviewed on the same day as they are reported by the study participant.
- Adverse effect assessment will be done by the research coordinators and discussed with the study physician on a daily basis, immediately after these adverse effects are reported by the participant to the study coordinator.

As with our current, CHR-approved clinical trials, the study physician, if not immediately present at the time of adverse effect data collection, will be contacted in real time by the study coordinator by phone, pager, or text message, so that adverse effects can be discussed with the study physician. The study physician, based on examination of the participant and/or review of the participant's data, will make a clinical judgment at each visit regarding whether it is safe to proceed with study medications.

The PI will report to the IRB, DSMB and study sponsor his assessment of the potential relatedness of each AE to protocol procedure, studied disease state, study drug via the CRF. For each adverse event recorded on the Adverse Event CRF, the PI will make an assessment of seriousness, severity, and causality.

According to the ICH guideline for Good Clinical Practice, an adverse event is any untoward medical occurrence in a clinical investigation participant administered a pharmaceutical product, regardless of causal attribution. An adverse event can therefore be any of the following:

- Any unfavorable and unintended sign (including an abnormal laboratory finding), symptom, or disease temporally associated with the use of a medicinal product, whether or not considered related to the medicinal product.
- Any new disease or exacerbation of an existing disease (a worsening in the character, frequency, or severity of a known condition).
- Recurrence of an intermittent medical condition (e.g., headache) not present at baseline.
- Any deterioration in a laboratory value or other clinical test (e.g., ECG, X-ray) that is associated with symptoms or leads to a change in study treatment or concomitant treatment or discontinuation from study drug. If a participant's dosage is reduced or treatment is discontinued as a result of an AE, the PI will report to the study sponsor via CRF the circumstances and data leading to any such dosage reduction or discontinuation of treatment.

Events leading to the clinical outcome of death from progressive disease will not be recorded as adverse events unless the PI believes that the event may have been caused by the study drug.

Serious adverse event (SAE) collection begins after the participant has signed informed consent and has received study drug. If a participant experiences an SAE after signing informed consent, but prior to receiving study drug, the event will NOT be collected unless the PI feels the event may have been caused by a protocol procedure.

The PI will alert the study sponsor of any SAE within 24 hours of the PI's awareness of the event. Alerts issued via telephone will be immediately followed with official notification on study-specific SAE forms.

An SAE is any adverse event from this study that results in one of the following outcomes:

- death (excluding death due to progression of study disease, unless related to study drug);
- initial or prolonged inpatient hospitalization;
- a life-threatening experience (that is, immediate risk of dying);
- persistent or significant disability/incapacity;
- congenital anomaly/birth defect;
- considered significant by the PI for any other reason.

Important medical events that may not result in death, be life-threatening, or require hospitalization may be considered serious adverse drug events when, based upon appropriate medical judgment, they may jeopardize the participant and may require medical or surgical intervention to prevent one of the outcomes listed in this definition.

Serious adverse events (SAEs) occurring after a participant has taken the last dose of study drug will be collected for 7 days after the last dose of study drug, regardless of the PI's opinion of causation. Thereafter, SAEs will not be reported unless the PI feels the events were related to either study drug, or drug delivery system, or a protocol procedure. Any SAE occurring prior to enrollment that the PI believes may have been caused by a protocol procedure will be reported to the study sponsor within 24 hours of the PI's awareness of the event and recorded on the CRF.

Study-specific clinical outcomes of death from progressive disease will be reported as SAEs only if the PI deems them related to use of the study drug.

Immediate Reporting Requirements From

PI to Sponsor:

Certain events will be immediately reported to allow the Sponsor to take appropriate measures to address potential new risks in a clinical trial. The PI will report such events to the Sponsor immediately; under no circumstances will be reporting take place more than 24 hours after the PI learns of the event. The following is a list of events that the PI will report to the Sponsor within 24 hours after learning of the event, regardless of relationship to study providers:

Serious adverse events

Non-serious adverse events of special interest

Pregnancies

The PI will report new significant follow-up information for these events to the Sponsor immediately (i.e., no more than 24 hours after becoming aware of the information). New significant information includes the following:

- New signs or symptoms or a change in the diagnosis;
- Significant new diagnostic test results;
- Change in causality based on new information;
- Change in the event's outcome, including recovery;
- Additional narrative information on the clinical course of the event.

Emergency Medical Contracts

Medical Monitor Contact Information:

Any life-threatening (i.e., imminent risk of death) or fatal AE that is attributed by the PI to the investigational product will be telephoned to the Medical Monitor immediately, followed by submission of written case details on an CRF within 24 hours.

The following is the contact information that will be utilized by the PI:

MEDICAL MONITOR

[name], MPH

SFVAMC/UCSF

[name]

[name]

[contact] [name]

Email: [contact]

Follow-up of Participants after Adverse Events

PI Follow-Up:

The PI will follow all unresolved treatment-related adverse event until the event has resolved to baseline grade or better, the event is assessed as stable by the PI, new therapy is initiated, the participant is lost to follow-up, or the participant withdraws consent.

Every effort will be made to follow all serious adverse events considered to be related to study procedures until a final outcome can be reported. During the study period, resolution of adverse events (with dates) will be documented on the Adverse Event CRF and in the participant's medical record to facilitate source data verification (SDV). If, after follow-up, return to baseline status or stabilization cannot be established, an explanation should be recorded on the Adverse Event CRF.

Data Review - For Phase II or III Sponsor Studies

PIs will conduct continuous review of data regarding participant safety at weekly study group meetings where the results of each participant's treatment are discussed, as is currently done for the PI's other UCSF CHR approved clinical trials. The discussion will include the number of participants, significant toxicities as described in the protocol, doses adjustments, and observed responses.

